7 SELECTION AND WITHDRAWAL OF SUBJECTS

The trial will include approximately 145 subjects from approximately 15 sites.

7.1 Inclusion Criteria

Subjects will be eligible for study participation if they:

- 1. Provide written informed consent prior to performing any study procedures and are willing to comply with study requirements and the study visit schedule.
- 2. Are 18 years of age or older.
- 3. Have a self-reported history or clinically confirmed diagnosis of DED by an eye care professional in both eyes for ≥ 6 months.
- 4. Have ongoing DED, in the study eye at screening visit as defined by the following criteria:
 - a. VAS eye dryness severity score of at least \geq 30.

In the same qualifying eye or both eyes:

- b A Total Corneal Fluorescein Staining Score of ≥ 6 (NEI scale) and <15.
- c. Have a Schirmer score (unanesthetized) of >0 mm and ≤ 10 mm wetting at 5 minutes.
- 5. Have corrected visual acuity better than or equal to logarithm of the minimum angle of resolution (logMAR), +0.7 as assessed with Early Treatment of Diabetic Retinopathy Study (ETDRS) charts in both eyes.
- 6. Are women of child-bearing potential (WOCBP) who are non-pregnant, non-lactating, and sexually inactive (abstinent) for 14 days prior to screening. And are willing to remain so through the last study visit. Alternatively, WOCBP who are not abstinent must have been using one of the following acceptable methods of birth control for the times specified:
 - a. Intra-uterine device (IUD) in place for at least 3 months prior to screening and the desire to continue this method through the last study visit.

- b. Barrier method (condom or diaphragm) with spermicide for at least 14 days prior to screening and the desire to continue this method through the last study visit.
- c. Stable hormonal contraceptive for at least 3 months prior to screening and the desire to continue this method through the last study visit.
- d. Surgical sterilization (vasectomy) of partner for at least 6 months prior to Day 1.
- 7. Are postmenopausal women [i.e., no menstrual cycle for at least one year prior to Visit 1 (Screening)] or are women who have undergone 1 of the following sterilization procedures at least 6 months prior to Visit 1 (Screening):
 - a. Bilateral tubal ligation
 - b. Hysterectomy
 - c. Hysterectomy with unilateral or bilateral oophorectomy
 - d. Bilateral oophorectomy
- 8. Agree to the removal of non-dissolvable punctal plugs 4 weeks prior to the insertion visit (Day 1, Visit 2). Long-term dissolvable punctal plugs were not placed within 4 months prior to insertion visit (Day 1, Visit 2) and short-term dissolvable punctual plugs were not placed within 6 weeks prior to insertion (Day 1, Visit 2).

7.2 Exclusion Criteria

Subjects are not eligible for study participation if they:

- 1. Have a known or suspected allergy to any component of the study product.
- 2. Are unwilling to discontinue use of contact lenses for 4 weeks prior to the screening visit and throughout the study period.
- 3. Have any active systemic disease and/or systemic infection (e.g., fever or current antibiotic use), or uncontrolled medical condition that in the judgment of the investigator could confound study assessments or limit compliance.
- 4. Have a documented history of ocular allergies, which, in the judgment of the investigator, are likely to have an acute increase in severity during the duration of this trial. Subjects sensitive to seasonal allergens that are not expected to be present during the study are permitted.
- 5. Have a history of neuropathic pain related to dry eye.
- 6. Have corneal erosive disease (e.g., multiple filaments, recurrent erosion syndrome) or other conditions suggestive of extensive damage of the cornea.
- Have a history of glaucoma or ocular hypertension or have intraocular pressure (IOP) < 5 mmHg or > 24 mmHg or a history of elevated IOP within the past 6 months prior to the screening visit.
- 8. Have abnormal lid anatomy that may confound study data, in the judgement of the investigator.
- 9. Have a diagnosis of any of the following:
 - a. Active ocular infection
 - b. Uveitis

c. Uncontrolled blepharitis (including severe MGD), in the judgement of the investigator Version 05, 03 June 2021 Page 31 of 76 Confidential

- d. Moderate to severe pinguecula or pterygia, in the judgement of the investigator
- e. Stevens-Johnson syndrome
- f. Mucous membrane pemphigoid
- g. Significant conjunctival scarring, in the judgement of the investigator
- h. Chemical burn
- i. Herpetic or neurotrophic keratitis
- j. Congenitally absent lacrimal gland or meibomian glands
- k. Nasolacrimal duct obstruction in either eye
- 10. Have had penetrating intraocular surgery in the past 6 months or require penetrating intraocular surgery during the study.
- 11. Have had eyelid surgery within 6 months prior to the screening visit.
- 12. Have had corneal laser refractive surgery, glaucoma surgery or corneal transplantation (full thickness, anterior or posterior).
- 13. Have had cauterization of the punctum resulting in complete occlusion of the punctum.
- 14. Have taken any of the following in either eye within 30 days prior to the screening visit:
 - a. Topical ocular cyclosporine (e.g., Cequa[®], Restasis[®])
 - b. Lifitegrast (Xiidra[®])
 - c. Autologous tears
 - d. Topical ocular corticosteroids
 - e. Topical ocular antibiotics
 - f. Topical ocular NSAID
 - g. Topical ocular antihistamines and/or mast cell stabilizers
 - h. Topical or nasal vasoconstrictors
 - i. Over The Counter (OTC) decongestants
 - j. Intranasal Tear Neurostimulation
- 15. Have taken any of the following in either eye prior to the screening visit:
 - a. Periocular injection of any corticosteroid solution 3 months
 - b. Corticosteroid intra-vitreal depot injection– 3 months
 - c. Ozurdex– 6 months
 - d. Retisert–40 months
- 16. Have altered the dose of the following within 30 days prior to the screening visit (i.e., should keep dose stable throughout the study):
 - a. Nutraceuticals or multivitamins
 - b. Tetracycline compounds (tetracycline, doxycycline or minocycline)
 - c. Inhaled, intramuscular or intra-articular corticosteroids (mouth or nasal spray form)

- 17. Have altered the dose of the following within 6 months prior to the screening visit (i.e., should keep dose stable throughout the study):
 - a. Systemic anticholinergics
 - b. Antidepressants (with the exception of rare usage as a sleep aid)
 - c. Oral corticosteroids (e.g., prednisone. Prednisone dose must be less than 11 mg/day)
- 18. Have taken isotretinoin (Accutane) or systemic immunosuppressive agents within 6 months prior to the screening visit.
- 19. Are unwilling to withhold use of artificial tears (AT) for the duration of the trial.
- 20. Have participated in any other investigational study within 30 days of the screening visit or plans to participate in any other investigational study during the follow-up period.
- 21. Are an employee of the site or an immediate family member of an employee of the site.
- 22. Are a current smoker (including marijuana, cigar, cigarette, and/or e-cigarettes).
- 23. Have a known history of alcohol and/or drug abuse or are currently using illicit drugs or plan to use illicit drugs for the duration of the study. Recreational or medicinal marijuana allowed if oral consumption (no inhaled use).
- 24. Are unwilling or unable to comply with the study protocol.
- 25. The Investigator determines that the subject should not be included for reasons not already specified (e.g., systemic, behavioral, or other ocular disease/abnormality) if the health of the subject or the validity of the study outcomes may be compromised by the subject's enrollment.

7.3 Entry/Randomization Criteria:

To qualify for insertion at Day 1 (Visit 2), a subject must continue to meet all screening inclusion/exclusion criteria with the following exceptions/additions:

- 1. VAS eye dryness severity score ≥ 25
- 2. CFS total score \geq 5 (NEI scale) and <15 in the same qualifying eye as Visit 1.
- 3. Subject must not have taken prohibited medications and have completed the appropriate washout of prior medications, if necessary.
- 4. Subjects who require AT use must not have administered >3 times/day for 3 consecutive days during the washout period (i.e. period between the screening and Day 1 visits.).

NOTE: AT use is not permitted unless absolutely necessary. If subject requires AT use and has administered >3 times/for 3 days during the Screening period, they are not eligible for randomization.

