7.5 Subject Recruitment and Screening

Each subject that is screened will be assigned a Subject Identification (ID) consisting of a 2-digit Site number plus a 3-digit Subject number. The Subject ID will be used as the primary subject identifier for the duration of the study. For Cohort 2, once all inclusion and exclusion criteria are met at Visits 1 and 2, each qualifying subject will be randomized via the IRT system and will be assigned a randomization number.

The subject must sign the Informed Consent Form (ICF) before his or her participation in the study. A copy of the ICF must be provided to the subject or the subject's legal guardian. If applicable, it will be provided in a certified translation of the subject's first or native language. The original signed ICF for each participating subject shall be filed with records kept by the investigator and must be available for verification by study monitors at any time, and a copy will be given to each subject.

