8.3.1 Visit 1 (14 days prior to Day 1) Screening/Baseline Visit

Note: In rare cases, the Screening Visit can be split into 2 consecutive days.

- Informed consent
- Demographics *
- Medical/ophthalmic history *
- Record concomitant medications *
- Urine pregnancy test * (may be performed at any time during the visit for WOCBP only)
- VAS for Eye Dryness (Appendix 3)
- OSDI (Appendix 4)
- SPEED assessment (Appendix 5)
- BCVA assessment (Appendix 8)
- Slit lamp biomicroscopy (including punctum assessment) (Appendix 9)
- TBUT (Appendix 11)
- Corneal fluorescein staining (NEI scale) (Appendix 6)

Conjunctival Lissamine Green Staining (NEI scale) (Appendix 7)

• Schirmer Test (without anesthesia) (Appendix 12)

Note: Wait 20 minutes prior to conducting Schirmer

- IOP
- Dilated fundus exam
- Determine Eligibility
- Dispense artificial tears (as needed)
 - **Note**: Subjects will be provided with sponsor supplied Preservative Free Artificial Tear Substitutes but instructed to use only if necessary. If used, instillation will be recorded in a daily diary. Subjects will also be asked to withhold the tears within two hours of study visits.
- Dispense Daily Subject Diary for Artificial Tears Use (as needed) (Appendix 16)

Note: All ophthalmic assessments must be performed on both eyes.

8.3.2 Visit 2 Insertion/Day 1

- Record concomitant medications *
- Record AEs

Note: Any signs, symptoms or conditions captured prior to the insertion of IP, will be recorded as medical history.

- Collect and review Subject Daily Diary for Artificial Tears Use (as needed)
 Note: Subjects using AT > 3x/day for 3 consecutive days will be ineligible for randomization.
- VAS for Eye Dryness
- OSDI
- SPEED assessment
- BCVA assessment
- Slit lamp biomicroscopy, including punctum assessment **Note:** Prior to insertion, a clinical determination of the absence of infection will be made based on the lack of erythema or discharge at the punctum.
- Punctum Size Assessment
- TBUT
- Corneal fluorescein staining (NEI scale)
- Conjunctival Lissamine Green Staining (NEI scale) Schirmer Test (without anesthesia)

Note: Wait 20 minutes prior to conducting Schirmer

- IOP
- Determine Eligibility for Insertion (Cohort 1 and 2) and Randomization (Cohort 2)
- OTX-CSI or HV Insert Placement (Appendix 13)
 Note: If placement is only successful in one eye, subjects should be asked to return within 0-3 days to re-attempt insertion in the other eye.
- Ease of Insertion Assessment

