8.3.9 Final Visit 8 (Week 16 ±3 days)

- Record concomitant medications *
- Record AEs *
- Collect and review Subject Daily Diary for Artificial Tear Use (as needed) *
- Urine pregnancy test (WOCBP only)
- VAS for Eye Dryness
- OSDI
- SPEED assessment
- BCVA assessment
- Slit lamp biomicroscopy, including punctum assessment
- OTX-CSI or HV Insert Presence by visual Assessment
- Ease of Visualization by Investigator
- Corneal fluorescein staining (NEI scale)
- Conjunctival Lissamine Green Staining (NEI scale)
- Schirmer Test (without anesthesia) and Tear Film PK

Note: Wait 20 minutes prior to conducting Schirmer/Tear Film PK

- Undilated Fundus Exam (*may be performed before or after IOP)
- IOP
- Punctum Size Assessment
- Dispense artificial tears (as needed)
- Dispense Daily Subject Diary for Artificial Tear Use (as needed)

Note: All ophthalmic assessments must be performed on both eyes.

8.3.10 30-day Follow-Up Visit (Week 20 ± 10 days)

This visit will be conducted every 30 days (\pm 10 days) until an insert can no longer be visualized and the physician has determined that there is no evidence of biological activity.

- Record concomitant medications *
- Record AEs *
- Collect and review Subject Daily Diary for Artificial Tear Use (as needed) *
- VAS for Eye Dryness
- OSDI
- SPEED assessment
- BCVA assessment
- Slit lamp biomicroscopy, including punctum assessment
- OTX-CSI or HV Insert Presence by visual Assessment
- Ease of Visualization by Investigator
- Corneal fluorescein staining (NEI scale)
- Conjunctival Lissamine Green Staining (NEI scale) Schirmer Test (without anesthesia) and Tear Film PK Note: Wait 20 minutes prior to conducting Schirmer/Tear Film PK
- Dispense artificial tears (as needed)
- Dispense Daily Subject Diary for Artificial Tear Use (as needed)

Note: All ophthalmic assessments must be performed on both eyes.

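### Women of child-bearing potential must still be non-pregnant at Day 1, but the only scheduled pregnancy test before insertion is at Visit 1, nominally 14 days earlier; a Visit 2 test would be a cheap, minor safety improvement

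*Protocol*

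**What the plan says.** **Eligibility at Day 1.** Protocol Section 7.3 applies to insertion in both cohorts: "a subject must continue to meet all screening inclusion/exclusion criteria with the following exceptions/additions". The four items that follow concern the VAS score, the corneal staining score, prohibited medications with washout, and artificial tear use. For Cohort 2, Section 7.5 adds that "once all inclusion and exclusion criteria are met at Visits 1 and 2, each qualifying subject will be randomized via the IRT system".

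**The pregnancy criterion.** Inclusion 6 in Section 7.1 begins: "Are women of child-bearing potential (WOCBP) who are non-pregnant, non-lactating, and sexually inactive (abstinent) for 14 days prior to screening". These women must also be willing to stay abstinent through the last study visit. WOCBP who are not abstinent must use a listed method:

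- an IUD in place for at least 3 months before screening, with the wish to continue;
- "Barrier method (condom or diaphragm) with spermicide for at least 14 days prior to screening", with the wish to continue;
- "Stable hormonal contraceptive for at least 3 months prior to screening and the desire to continue this method through the last study visit";
- a partner's vasectomy at least 6 months before Day 1.

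**The tests.** Section 8.3.1 lists a urine pregnancy test for WOCBP at Visit 1, and Section 8.3.9 lists one at Visit 8. The Visit 2 list (8.3.2) and the Visit 2B list (8.3.3) contain none. Appendix 1, SAP Table 1 and SAP Section 4.9.1 show the same two time points. Footnote 1 of Appendix 1 requires a negative test for inclusion but does not tie it to insertion.

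**The concern.** Visit 2 has its own formal step for deciding eligibility for insertion and randomisation. VAS, visual acuity, corneal staining, Schirmer and IOP are all measured again before that step. Pregnancy status is a criterion that must still hold, it has a simple objective test that the trial already uses, and it is not checked again.

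What is at stake is subject safety; the efficacy results are not affected. Day 1 is the dosing decision: Section 8.1 describes one insertion releasing drug over approximately 12 weeks. A pregnancy that the subject knows of or reports would bar insertion under Section 7.3. The gap concerns an unrecognised one. After insertion, detection rests on the subject telling the investigator (Section 10.9.1) or on an optional test at an unscheduled visit (Section 8.3.12), until the Week 16 test.

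**Working it through.** The plan gives no figure to reproduce. The check sets the schedule against the eligibility rule and then asks what a Day 1 test would add.

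**Step 1: where the tests fall.** Nominal days, with Visit 1 at 14 days before Day 1 (8.3.1; no window is stated) and Visit 8 at Week 16 ± 3 days (8.3.9).

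| Point | Eligibility decided? | Urine pregnancy test scheduled? |
|---|---|---|
| Visit 1 | Yes | Yes |
| Visit 2, insertion | Yes | No |
| Visit 2B, second attempt after a unilateral insertion | No | No |
| Visits 3 to 7 | No | No |
| Visit 8 | No | Yes |

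**Step 2: the intervals.**

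- Last scheduled test to insertion: 14 days.
- Insertion to next scheduled test: 16 × 7 = 112 days.
- Between the two scheduled tests: 14 + 112 = 126 days.
- Designed release: about 12 × 7 = 84 days, so the Week 16 test comes about 112 − 84 = 28 days after designed release ends.
- With a Visit 2 test: 0 days from test to insertion. The 112 days after insertion are unchanged.

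**Step 3: which pregnancies a Visit 2 test could find.** The documents give no sensitivity for the urine test. The only assumption here is that detectability rises with time since conception.

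| Conception | Age at Visit 1 | Age at Day 1 | What a Visit 2 test adds |
|---|---|---|---|
| More than 14 days before Visit 1 | Over 14 days | Over 28 days | Little: the Visit 1 test has the better chance here |
| In the 14 days before Visit 1 | 0 to 14 days | 14 to 28 days | Most of the gain: may be missed at Visit 1 and found at Day 1 |
| Between Visit 1 and Day 1 | Not yet begun | 0 to 14 days | Limited: many would still be too recent |

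**Step 4: who could be in the middle row.** A woman who complied by abstinence had no exposure in the 14 days before screening, so she is unlikely to be there. For users of a contraceptive method, a pregnancy in that row needs a method failure. Barrier users need only 14 days of use before screening; IUD and hormonal users need 3 months. For the last row, the stated intention to continue abstinence, IUD, barrier or hormonal contraception covers the interval from Visit 1 to Day 1, although it is a commitment and not a test.

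**Step 5: the number of cases.** It cannot be computed. The documents give neither the share of WOCBP among the roughly 145 subjects nor a contraceptive failure rate.

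**The case against.** The strongest reply is that nothing in the plan is violated. Continuing to meet a criterion does not mean that each criterion is tested again: medical history and the fundus examination are also done at screening and not repeated at Visit 2. The Visit 1 test satisfies footnote 1 of Appendix 1, and the protocol and SAP schedules agree. All of this stands. A reader might infer from Sections 7.3 and 7.5 that the protocol contradicts its own schedule; the documents do not support that reading. This is a design choice that could be improved.

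A second reply is that the plan's control for this interval is contraception. That is largely right, and it is why the residual risk is low. It lowers the chance of pregnancy but does not verify status on the day of dosing. Sites also ask about adverse events at each visit, and the investigator may exclude a subject on health grounds (Exclusion 25), but neither is a pregnancy test.

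A third reply is that the added yield is narrow and that the longer untested interval, 112 days after insertion, is untouched. Both are true. A reader might take the fall from 14 days to 0 to mean that the detection gap closes. It does not; only the interval from test to insertion becomes 0.

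Finally, a reader might infer that the insert is known to be harmful in pregnancy. The documents report no reproductive-harm data for it, and none is claimed here. The comparisons with oral cyclosporine dosing in Section 4.5 measure neither the chance of pregnancy nor reproductive safety, so they do not decide the point in either direction. The insert can be removed (Appendix 15), although Section 4.4 lists inability to remove it among the observed risks.

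**Conclusion.** The point holds as a minor safety improvement. In both cohorts, non-pregnancy must still hold at Day 1, and the only scheduled pre-insertion test is nominally 14 days old by then, with the next at Week 16. The schedule facts are certain from the documents. The importance is small: the residual risk is low under Inclusion 6, the number of cases cannot be estimated, and no efficacy analysis is affected. The benefit of a Visit 2 test lies mainly in pregnancies present but undetectable at Visit 1. This rests on the nominal 14-day screening interval and on the general assumption that a urine test becomes more likely to be positive as a pregnancy advances.

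**What to change.** Add a urine pregnancy test for WOCBP to the Visit 2 list in Section 8.3.2, placed before the eligibility step and before randomisation, and mark it at Visit 2 in Appendix 1. Align SAP Table 1 and SAP Section 4.9.1 so that results are captured at Visits 1, 2 and 8. The order matters: a positive result before randomisation is a screen failure, whereas one found after it would leave a randomised, untreated subject in the ITT population.

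The cost is one dipstick per WOCBP at an existing visit, one line in 8.3.2, one entry in each schedule table, a small edit to SAP 4.9.1, and an occasional extra screen failure. The change will still miss very recent conceptions and does not add testing between insertion and Week 16.

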7.4 Procedural Exclusion Criteria

Subjects are considered procedural screen failures if the investigator is unsuccessful at placing the OTX Ophthalmic insert in both eyes (i.e. neither eye has an insert). Procedural screen failures will be exited from the study at that time and will be included in the disposition tables as 'randomized, not treated'. Subjects will be followed per protocol if the investigator successfully places one insert.

Note: A subject with a successful unilateral insertion should return within three days to re-attempt insertion in the unsuccessful eye.

7.5 Subject Recruitment and Screening

Each subject that is screened will be assigned a Subject Identification (ID) consisting of a 2-digit Site number plus a 3-digit Subject number. The Subject ID will be used as the primary subject identifier for the duration of the study. For Cohort 2, once all inclusion and exclusion criteria are met at Visits 1 and 2, each qualifying subject will be randomized via the IRT system and will be assigned a randomization number.

The subject must sign the Informed Consent Form (ICF) before his or her participation in the study. A copy of the ICF must be provided to the subject or the subject's legal guardian. If applicable, it will be provided in a certified translation of the subject's first or native language. The original signed ICF for each participating subject shall be filed with records kept by the investigator and must be available for verification by study monitors at any time, and a copy will be given to each subject.

7.6 Withdrawal Criteria

Any subject who wishes to voluntarily discontinue study drug or withdraw from participation in the study for any reason is entitled to do so without obligation.

IP may be discontinued (insert removed) and any subject may be discontinued from study participation at any time during the study at the discretion of the Investigator or the Sponsor for any reason.

